5.2.2 Subsequent Days (Chemoradiation)

Prior to administration of the subsequent doses of bavituximab during chemoradiation participants must meet the following criteria. Patients can continue bavituximab if temozolomide is held for temozolomide related toxicity:

- Platelet count \geq 75,000/mcL
- WBC \geq 2,500/mcL
- No other bavituximab treatment related toxicities CTCAE grade > 2 (except for not maximally treated nausea and vomiting)
- If a bavituximab cannot be administered because of toxicity, there is a +3 day window to treat, otherwise the dose will be skipped and the patient resume dosing the next week if criteria met.
- 5.2.3 Subsequent Cycles of temozolomide (Post-chemoradiation cycles) Prior to administration of the subsequent doses of temozolomide participants must meet the following criteria within the windows outlined in the Study Calendar in Section 10:
 - Resolution of all grade 3 non-hematologic AEs (except for not maximally treated nausea and vomiting) to grade ≤ 1
 - Absolute neutrophil count (ANC) < grade 2
 - Platelet count \geq 100,000/mcL
 - Hemoglobin $\geq 8.0 \text{ g/dL}$
 - White blood cell (WBC) count $\geq 2,500/mcL$

- AST/SGOT and ALT/SGPT ≤ 2.5 x upper limit of normal (ULN)
- Serum total bilirubin ≤ 1.5 x ULN (unless patient has Gilbert's syndrome in which total bilirubin should be ≤ 2 xULN)
- Serum creatinine $\leq 1.5 \text{ x ULN}$ or 24-hour creatinine clearance $\geq 60 \text{ ml/min}$
- No other temozolomide related toxicities CTCAE grade >2
- If AEs persist, the start of the cycle may be delayed up to 30 consecutive days. If all AEs have not resolved to grade ≤ 1 after a 30-day delay, any further study treatment will be discontinued.
- For C3 and C4 when monthly temozolomide starts, bavituximab should be administered within 5 days of Day 1 of the temozolomide
- 5.2.4 Subsequent Cycles of bavituximab (Post-chemoradiation cycles)

Prior to administration of the subsequent doses of bavituximab participants must meet the following criteria within the windows outlined in the Study Calendar in Section 10. Patients can continue bavituximab if temozolomide is held for temozolomide related toxicity:

- Resolution of all grade 3 non-hematologic AEs (except for not maximally treated nausea and vomiting) to grade ≤ 2 thought related to bavituximab
- Platelet count \geq 75,000/mcL
- Hemoglobin $\ge 8.0 \text{ g/dL}$
- White blood cell (WBC) count $\geq 2,500/mcL$
- AST/SGOT and ALT/SGPT ≤ 2.5 x upper limit of normal (ULN)
- Serum total bilirubin ≤ 1.5 x ULN (unless patient has Gilbert's syndrome in which total bilirubin should be ≤ 2 xULN)
- Serum creatinine $\leq 1.5 \text{ x ULN}$ or 24-hour creatinine clearance $\geq 60 \text{ ml/min}$
- No other bavituximab related toxicities CTCAE grade > 2
- If AEs persist, the start of the cycle may be delayed up to 30 consecutive days. If all AEs have not resolved to grade < 2 after a 30-day delay, any further study treatment will be discontinued.
- For C3 onwards when monthly temozolomide starts, bavituximab should be administered within 7 days of Day 1 of the temozolomide

5.3 Agent Administration

5.3.1 CTEP and/or CIP IND Agent(s), or other IND agent: Bavituximab

Administration: Bavituximab will be administered IV.

Dosing: Bavituximab dose is 3 mg/kg body weight. The total dose is only required to be recalculated if there is a $\geq 10\%$ change in weight from Day 1 or per institutional policy. There will otherwise be no modification of dose level or schedule of bavituximab treatment. Bavituximab will be given weekly +/- 3 days.

If infusion is not administered within this window, it is considered skipped and dosing

will resume at next scheduled time.

Infusion Reactions: Administer standard hypersensitivity reaction medications per institution guidelines. In addition, all patients should be pre-medicated as outlined in Section 5.

Clinically mild reactions (eg, generalized rash or itching, hives) are treated as soon as possible with Benadryl® (diphenhydramine hydrochloride) 25 to 50 mg, orally or IV at the investigator's discretion. The period of observation is extended beyond 3 hours, as necessary, until symptoms and signs have resolved or stabilized. Patients who have experienced a clinically mild reaction may continue to have study drug administered.

Clinically moderate reactions (eg, hypotension, shortness of breath, presyncope, facial edema) are treated immediately and supportive care measures instituted as medically indicated (eg, IV fluids, corticosteroids, vasopressors, oxygen, bronchodilators, diphenhydramine, and acetaminophen). Vital signs are monitored at 10-minute intervals until they have normalized. The period of observation is extended beyond 3 hours, if necessary, until symptoms and signs have resolved. In the event of a clinically moderate reaction, the patient should receive no further treatment with study drug.

For grade 3-4 reactions, halt infusion and discuss with principle investigator if rechallenge is reasonable or if the patient should go off treatment.

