7.1 Expected Toxicities

7.1.1 Adverse Events List(s)

7.1.1.1 Adverse Event List(s) for bavituximab

Table 24:

Treatment-emergent Adverse Events Occurring in More Than 5% of Patients Treated with Bavituximab and Chemotherapy by Preferred Term and Dose Level for all Oncology Studies Safety Population

	Number of Patients(%)			
	Oncology ^a		Total	
Preferred Term	1 mg/kg ^b (N=79)	3 mg/kg (N=570)	Total (N=649)	
Alopecia	14 (17.7%)	174 (30.5%)	188 (29.0%)	
Nausea	21 (26.6%)	167 (29.3%)	188 (29.0%)	
Fatigue	21 (26.6%)	162 (28.4%)	183 (28.2%)	
Diarrhoea	15 (19.0%)	166 (29.1%)	181 (27.9%)	
Neutropenia	18 (22.8%)	149 (26.1%)	167 (25.7%)	
Anaemia	14 (17.7%)	145 (25.4%)	159 (24.5%)	
Asthenia	13 (16.5%)	121 (21.2%)	134 (20.6%)	
Cough	17 (21.5%)	103 (18.1%)	120 (18.5%)	
Dyspnoea	11 (13.9%)	106 (18.6%)	117 (18.0%)	
Pyrexia	13 (16.5%)	101 (17.7%)	114 (17.6%)	
Vomiting	9 (11.4%)	103 (18.1%)	112 (17.3%)	
Constipation	12 (15.2%)	95 (16.7%)	107 (16.5%)	
Leukopenia	12 (15.2%)	85 (14.9%)	97 (14.9%)	
Decreased appetite	5 (6.3%)	84 (14.7%)	89 (13.7%)	
Oedema peripheral	16 (20.3%)	66 (11.6%)	82 (12.6%)	
Arthralgia	8 (10.1%)	71 (12.5%)	79 (12.2%)	
Back pain	8 (10.1%)	70 (12.3%)	78 (12.0%)	
Headache	8 (10.1%)	61 (10.7%)	69 (10.6%)	
Pain in extremity	8 (10.1%)	61 (10.7%)	69 (10.6%)	
Anorexia	12 (15.2%)	48 (8.4%)	60 (9.2%)	
Stomatitis	4 (5.1%)	55 (9.6%)	59 (9.1%)	

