7.1.1.2 Adverse Event List(s) for Other Agent(s)

Please see package insert for adverse events for temozolomide.

7.2 **Adverse Event Characteristics**

CTCAE term (AE description) and grade: The descriptions and grading scales found • in the revised NCI Common Terminology Criteria for Adverse Events (CTCAE) version 4.0 will be utilized for AE reporting. All appropriate treatment areas should have access to a copy of the CTCAE version 4.0. A copy of the CTCAE version 4.0 can be downloaded from the CTEP web site http://ctep.cancer.gov/protocolDevelopment/electronic applications/ctc.htm.

For expedited reporting purposes only: •

- AEs for the agent(s) that are listed above should be reported only if the adverse event varies in nature, intensity or frequency from the expected toxicity information which is provided.
- Other AEs for the protocol that do not require expedited reporting are outlined in the next section (Expedited Adverse Event Reporting) under the sub-heading of Protocol-Specific Expedited Adverse Event Reporting Exclusions.
- Attribution of the AE:

- Definite The AE *is clearly related* to the study treatment.
- Probable The AE *is likely related* to the study treatment.
- Possible The AE *may be related* to the study treatment.
- Unlikely The AE is doubtfully related to the study treatment.
- Unrelated The AE is clearly NOT related to the study treatment.

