8.1.8 Administration

DO NOT ADMINISTER TREATMENT AS AN IV PUSH OR BOLUS.

Pre-medication is no longer required prior to bavituximab administration as the steroids may interfere with drug efficacy and there have been limited reactions in patients so far. If pre-medication is warranted, one possible regimen is 250 mg hydrocortisone IV and 25-50 mg diphenhydramine IV administered ideally 30 minutes prior to infusion; regimen, dosages, and timing can be adjusted at the investigator's discretion. Patients receiving premedication for other therapy do not require additional corticosteroids on days when both are administered. Patients who tolerate bavituximab without reaction may not need pre-medication with subsequent doses and pre-medication use can be decided in conjunction with patient, nursing, treating physician.

Affix the infusion line and prime it with infusate before starting the infusion. The first IV infusion must be administered over approximately 90 (± 10) minutes. Patients should be watch for 180 minutes after the start of the first infusion. If the first IV infusion is tolerated, subsequent infusions may be administered over 60 minutes with no post-infusion observation as long as no hypersensitivity reactions occur.

Flush the main infusion line with normal saline after infusion.

NOTE: Bavituximab should only be administered in settings in which emergency

resuscitative equipment and personnel trained in the management of anaphylaxis are immediately available to treat systemic hypersensitivity reactions.

NOTE: These instructions must be consistent with protocol section 5: TREATMENT PLAN.

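### Section 5.3.1 ends bavituximab after a clinically moderate infusion reaction but leaves rechallenge open after a grade 3-4 reaction, and nothing links the two scales

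*Combined protocol and SAP*

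**What the plan says.** Section 5.3.1 (Infusion Reactions) sets three rules.

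- **Mild:** dosing may continue.
- **Moderate:** the tier is described by example symptoms and has no grade: "Clinically moderate reactions (eg, hypotension, shortness of breath, presyncope, facial edema) are treated immediately". The supportive measures listed are "IV fluids, corticosteroids, vasopressors, oxygen, bronchodilators, diphenhydramine, and acetaminophen". The consequence is "In the event of a clinically moderate reaction, the patient should receive no further treatment with study drug".
- **Grade 3-4:** "For grade 3-4 reactions, halt infusion and discuss with principle investigator if rechallenge is reasonable or if the patient should go off treatment".

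There is no clinically severe tier. Section 6 applies CTCAE v4.0 to dose delays and modifications. Section 7.2 applies it to safety reporting: "Common Terminology Criteria for Adverse Events (CTCAE) version 4.0 will be utilized for AE reporting". Neither section connects a CTCAE grade to the words mild or moderate.

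**The concern.** The rule decides whether a patient is re-exposed to a chimeric antibody after a reaction to it, and staff have to apply it at the infusion chair. As written, the permanent stop is attached to the moderate tier, and the option to try again is attached to the tier labelled grade 3-4. Two sites could handle the same event differently depending on which label they chose. The error can run either way: re-exposure after a severe reaction, or automatic loss of the drug after a lesser one.

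**Working it through.** No formula underlies the rule and the plan gives no figure to reproduce, so the main check is a reading of the text. A short scenario for size follows.

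**1. The two possible readings.** They are alternatives and cannot both hold for the same event.

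| Reading | Moderate reaction | Grade 3-4 reaction | Result |
|---|---|---|---|
| A. Moderate lies below grade 3 | Stop permanently | Halt; rechallenge possible | Stricter rule for the milder reaction |
| B. Moderate can reach grade 3-4 | Stop permanently | Halt; rechallenge possible | Two instructions for one patient |

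Reading B is plausible because the moderate tier has no upper bound. Hypotension is among its examples, and vasopressors and oxygen are among its treatments. The text of CTCAE v4.0 is not in the documents, so it cannot settle the choice. Equating moderate with grade 2 would simply give reading A.

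**2. Does another section resolve it?**

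- Section 5.2.2 (during chemoradiation): no bavituximab-related toxicity above grade 2 before a further dose. Outside a 3-day window the dose is skipped and dosing resumes the next week if the criteria are met.
- Section 5.2.4 (after chemoradiation): the same threshold, with a delay of up to 30 days, after which unresolved toxicity ends study treatment. It also expects grade 3 non-hematologic events related to bavituximab to settle to grade 2 or less before redosing, so it contemplates redosing after a resolved grade 3 event.
- Section 5.5: therapy ends for unacceptable adverse events or on investigator judgment. No grade is given.
- Section 6: CTCAE v4.0 governs dose modification, but the tables concern temozolomide and none covers infusion reactions.
- Section 8.1.8: premedication, infusion time, observation and emergency readiness. It gives no mapping.
- Section 12.2: committee review of toxicity, and a halting rule for unexpected toxicity of grade 4 or higher. It does not direct the care of an individual patient.

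A grade 3 reaction that has settled by the next weekly dose therefore passes Sections 5.2.2 and 5.2.4, while a moderate reaction is barred by Section 5.3.1.

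**3. Size.** The patients concerned are those with a grade 3-4 or overlapping reaction. A reaction that is clearly moderate and clearly below grade 3 has an unambiguous instruction.

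- n = 33 evaluable patients (Section 13.1), up to 36 enrolled.
- p = rate of grade 3-4 or overlapping reactions per patient. The documents give none, so the values below are assumptions.
- Expected patients = n × p. Chance of at least one = 1 − (1 − p)^n.

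| Assumed p | Expected of 33 | Chance of at least one |
|---|---|---|
| 0.5% | 0.17 | 15% |
| 1% | 0.33 | 28% |
| 2% | 0.66 | 49% |
| 5% | 1.65 | 82% |

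With n = 36 the expected counts are 0.18, 0.36, 0.72 and 1.80.

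The documents say little about where p lies. The table in Section 7.1.1.1 is titled "Treatment-emergent Adverse Events Occurring in More Than 5% of Patients Treated with Bavituximab and Chemotherapy by Preferred Term". As supplied it shows no infusion-reaction term, and its lowest row is 59/649 = 9.1%. Because it stops above its own 5% cut-off it may be incomplete. It also covers all grades, so 9.1% is neither a ceiling nor an estimate for p. Section 8.1.8 says "there have been limited reactions in patients so far". Section 2.2 reports infusion reactions as the most common bavituximab-related event in a 14-patient breast cancer study, without grades, and no grade 4 or 5 events in the 38-patient hepatocellular study.

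**The case against.** The strongest reply is that every grade 3-4 reaction already has a mandatory halt and a named decision-maker. Redosing is blocked while toxicity exceeds grade 2. Serious events go to the Overall PI (Section 7.3.1), Section 8.1.8 requires that "personnel trained in the management of anaphylaxis are immediately available to treat systemic hypersensitivity reactions", and a safety committee reviews toxicity. On reading B, one could add that the moderate rule already bars further drug and that the grade 3-4 sentence only adds the halt and the discussion. Few patients are likely to be involved.

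Most of this stands, and it limits the harm. It does not say which rule applies. The grade 3-4 sentence expressly keeps rechallenge open, so it does more than add steps to a stop rule, and the redosing criteria no longer bind once the reaction resolves.

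A reader might infer three stronger things that the documents do not support:

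- **That the protocol directs re-exposure after severe reactions.** It leaves that to discussion, and going off treatment is one of the two outcomes named.
- **That the rule is both inverted and self-contradictory.** These follow from different readings of moderate, and the text does not settle which is meant.
- **That the chance of any moderate-or-worse reaction measures the problem.** That count includes patients whose instruction is clear.

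**Conclusion.** The concern holds on the text. Section 5.3.1 gives either a more permissive rule for the more severe reaction or two incompatible rules for one event, and no other section resolves it. It should be fixed because it is a stated safety rule on re-exposure. It does not threaten the trial's conclusions.

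The size rests on assumption. At rates of 0.5% to 5%, about 0.2 to 1.7 of 33 patients would have a reaction for which the defect matters. The lower end looks more plausible given the sparse severity data, but nothing in the documents measures it.

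A reader might also infer an effect on the primary analysis. There is none in the design: the primary analysis is by intention to treat (Section 13.5.2), vital status at 12 months is sought whether or not dosing continues, and the OS12 sample size, alpha and power do not depend on this rule.

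**What to change.** In Section 5.3.1, define all infusion-reaction tiers by CTCAE v4.0, the scale already adopted in Sections 6 and 7.2, and state which grades the mild and moderate tiers cover. Make the consequence of a grade 3-4 reaction at least as strict as that of a moderate one.

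The simplest form that keeps the existing moderate rule is permanent discontinuation of bavituximab after any moderate or grade 3-4 reaction. That is partly a clinical choice, because the documents do not show which sentence expresses the intent. If the sponsor wishes to keep rechallenge, Section 5.3.1 should state its criteria and should not treat moderate reactions more strictly than grade 3-4 reactions.

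The cost is one wording amendment and a note to treating teams, with no change to sample size, data collection or analysis. Under the simplest form, a few patients lose the option of rechallenge.

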5.3.2 Other Agent(s)

Temozolomide will be taken per standard of care. Guidelines provided below on dosing/schedule.

Temozolomide During Concomitant Radiation Therapy

Temozolomide will be administered continuously from day 1 of radiotherapy to the last day of radiotherapy at a daily oral dose of 75 mg/m² for a maximum of 42 days. The drug will be administered orally 1-3 hours before each session of radiotherapy during weekdays (Monday through Friday). During weekends without radiotherapy (Saturday and Sunday), the drug will be taken in the morning. The dose will be determined using actual body surface area (BSA) as calculated in square meters at the beginning of the concomitant treatment.

Patients will be instructed to swallow the capsules whole, in rapid succession, without chewing them. If vomiting occurs during the course of treatment, no re-dosing of the patient is allowed before the next scheduled dose. The capsules should be taken on an empty stomach, therefore a minimum of 2 hours after eating and with no food consumption for at least 1 hour after temozolomide administration. Although, nightly administration just before bedtime has been reported to improve tolerance, the low daily dose administered during radiation is very well tolerated and administration in the morning before radiation dosing is required for this protocol. Administration of the higher dosing regimen during the adjuvant phase of the protocol should be performed using the nightly administration.

Antiemetic prophylaxis is usually not required for the continuous daily dosing schedule (during radiation). However, prophylaxis with a 5-HT3 antagonist is recommended 30-60 minutes prior to administration of the first few temozolomide doses. Most patients report optimal nausea control with the use of a 5-HT3 antagonist. Routine use of antiemetics is recommended during the adjuvant phase of treatment. Additionally, pneumocystis carinii prophylaxis is at the discretion of the Investigator during the radiation phase.

Post-Radiation Temozolomide Dosing

As part of this protocol, patients will receive up to 2 cycles of adjuvant temozolomide at a dose of 150-200 mg/m2 days 1-5 of a 28-day cycle. Patients will be treated for up to 6 months of post-RT temozolomide (Stupp 2005). If patients experience grade 3 or higher toxicity attributable to the temozolomide that does not resolve to a grade 2 or less within 60 days of the last temozolomide dose, temozolomide should be discontinued. If the toxicity returns to a grade 2 or less within 30 days of the last dose, temozolomide can be dose reduced to 150mg/m2. The active period of this clinical trial will be approximately 18 weeks as long as there are no delays or missed doses that need to be made up.

As part of this protocol, temozolomide will be administered orally once per day for 5 consecutive days (days 1-5) of a 28-day cycle. The starting dose for the first cycle will be 150 mg/m²/day, with a single dose escalation to 200 mg/m²/day in subsequent cycles if no treatment-related adverse events > Grade 2 are noted. Patients can be increased to 200 mg/m2 at any time during the maintenance phase if deemed clinically appropriate by the treating physician.

The start of the cycle 2 will be scheduled 28 days \pm 7 days after the last day of radiotherapy. The start of the subsequent cycles (Cycles 3-4) will be scheduled in 28 days \pm 7 days) after the first daily dose of temozolomide of the preceding cycle.

The dose will be determined using the BSA per institutional standard.

Patients will be instructed to fast at least 2 hours before and 1 hour after temozolomide administration. Water is allowed during the fast period. Patients will be instructed to swallow the capsules whole, in rapid succession, without chewing them. Treatment can be given at night if patient prefers.

If vomiting occurs during the course of treatment, no re-dosing of the patient is allowed before the next scheduled dose.

If a patient misses the dose of temozolomide, it made be made up within 8 hours, otherwise the dose should be delayed until the next time it is due. Missed doses can be added on to the end of the 5 day dosing (i.e. taken on day 6) during the maintenance phase (i.e. 5/28 day cycles).

Antiemetic prophylaxis with a 5-HT3 antagonist is recommended and should be administered 30 to 60 minutes before temozolomide administration. Temozolomide should be stored at room temperature.

5.3.3 Other Modality(ies) or Procedures

Radiation will be delivered per standard of care guidelines which includes 60 GY of involved field radiation delivered in up to 2 Gy fractions per day over 6 weeks.

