6. DOSING DELAYS/DOSE MODIFICATIONS

Dose delays and modifications will be made as indicated in the following table(s). The descriptions and grading scales found in the revised NCI Common Terminology Criteria for Adverse Events (CTCAE) version 4.0 will be utilized for dose delays and dose modifications. A copy of the CTCAE version 4.0 can be downloaded from the CTEP website http://ctep.cancer.gov/protocolDevelopment/electronic_applications/ctc.htm.

If temozolomide is held, bavituximab can continue if the adverse event is deemed to be unlikely related to bavituximab. There will be no change in dosing schedule or assessment schedule if either drug is held.

Nausea	Management/Next Dose for temozolomide
≤ Grade 1	No change in dose
Grade 2	Hold until \leq Grade 1. Resume at same dose level.
Grade 3	Hold [*] until < Grade 2. Resume at one dose level lower, if indicated. ^{**}

Nausea	Management/Next Dose for temozolomide		
Grade 4	Off protocol therapy		
*Participants requiring a delay of >30 days should go off protocol therapy.			
**Participants requiring > two dose reductions should go off protocol therapy.			
Recommended manag	ement: antiemetics.		

Vomiting	Management/Next Dose for temozolomide
≤ Grade 1	No change in dose
Grade 2	Hold until \leq Grade 1. Resume at
	same dose level.
Grade 3	$Hold^*$ until < Grade 2. Resume at
	one dose level lower, if indicated.**
Grade 4	Off protocol therapy
*Participants requiring	a delay of >30 days should go off pr
**Participants requirin	g > two dose reductions should go of
Recommended manag	gement: anti-emetics.

Neutropenia	Management/Next Dose for temozolomide	
\leq Grade 1	No change in dose	
Grade 2	Hold until \leq Grade 1. Resume at	
Ofade 2	same dose level.	
Grade 3	$Hold^*$ until < Grade 2. Resume at	
Glade 5	one dose level lower, if indicated.**	
Grade 4	Off protocol therapy	
	g a delay of >30 days should go off pro	
*Participants requirin	g > two dose reductions should go off	f protocol therapy

Thrombocytopenia	Management/Next Dose for temozolomide		
\leq Grade 1	No change in dose		
Grade 2	Hold until \leq Grade 1. Resume at same dose level.		
Grade 3	Hold [*] until < Grade 2. Resume at one dose level lower, if indicated. ^{**}		
Grade 4	Off protocol therapy		
*Participants requiring a delay of >30 days should go off protocol therapy. **Participants requiring > two dose reductions should go off protocol therapy.			

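### Sections 5.2.3, 5.3.2 and 6 conflict on the same temozolomide toxicity: recovery grade, what is stopped, grade 4 events and, in narrower cases, the time limit and reduced dose

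*Combined protocol and SAP*

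**What the plan says.** **Section 5.3.2, post-radiation dosing.** For toxicity of grade 3 or higher attributed to temozolomide "that does not resolve to a grade 2 or less within 60 days of the last temozolomide dose, temozolomide should be discontinued". The next sentence adds: "If the toxicity returns to a grade 2 or less within 30 days of the last dose, temozolomide can be dose reduced to 150mg/m2". The same section sets the first post-radiation course at 150 mg/m2 per day, with one possible step up to 200.

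**Section 5.2.3, criteria for starting a post-radiation temozolomide cycle.** Grade 3 non-haematological events must have come down to grade 1 or less (nausea and vomiting not yet maximally treated are excepted). A later line reads "No other temozolomide related toxicities CTCAE grade >2". Then: "If AEs persist, the start of the cycle may be delayed up to 30 consecutive days". If all events are not at grade 1 or less "after a 30-day delay, any further study treatment will be discontinued".

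**Section 6, temozolomide tables for nausea, vomiting, neutropenia and thrombocytopenia.** Grade 3 is held until below grade 2 and restarted one dose level lower if indicated. Grade 4 means off protocol therapy. A footnote adds: "Participants requiring a delay of >30 days should go off protocol therapy". The dose-level table gives 150 mg/m2 as level 0, 200 as level +1 and 100 as level -1, the level for prior toxicity.

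**Bavituximab during a hold.** Section 6 states: "If temozolomide is held, bavituximab can continue if the adverse event is deemed to be unlikely related to bavituximab". Sections 5.2.2 and 5.2.4 say much the same.

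**The concern.** All three sections decide the same thing: what happens to a patient with temozolomide toxicity after radiation. Two investigators following different sections could treat identical patients differently. One would keep the patient on bavituximab; the other would end all study treatment.

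The rules will be used. Section 12.2 cites temozolomide toxicities, including these four, at rates as high as 46% of patients (grade not stated). At stake are patient safety, the amount of bavituximab behind the results, and the off-treatment date and reason that Section 5.5 requires to be recorded.

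**Working it through.** No design figure depends on this point, so there is nothing of the plan's to reproduce first. The check sets the rules side by side and then puts the time limits on one scale.

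| | 5.3.2 | 5.2.3 | Section 6 tables |
|---|---|---|---|
| Recovery required | grade 2 or less | grade 1 or less | below grade 2 (for grade 3) |
| Limit | 60 days from last dose | 30 days' delay of cycle start | delay over 30 days |
| What ends | temozolomide; bavituximab not mentioned | any further study treatment | participant's protocol therapy |
| Grade 4 | same rule as grade 3 | no separate rule | off protocol therapy (four listed toxicities) |
| Reduced dose | 150 mg/m2 | none stated | one level lower; level -1 is 100 |

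**1. Recovery grade.** Take a grade 3 non-haematological event that falls to grade 2 and stays there. Under 5.3.2 it has recovered. Under 5.2.3 it fails the first start criterion, the cycle is delayed, and after 30 days all study treatment ends. The other line in 5.2.3, which tolerates up to grade 2, makes that section harder to apply.

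**2. What is stopped.** Suppose temozolomide must stop for good. Section 5.3.2 ends temozolomide and says nothing of bavituximab. Section 5.2.3 says "any further study treatment will be discontinued", and Section 6 ends protocol therapy.

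**3. Grade 4.** Section 5.3.2 covers grade 3 or higher, so grade 4 thrombocytopenia has up to 60 days to recover. The Section 6 table takes that patient off protocol therapy on grade alone.

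**4. Time limit, on one clock (days since last temozolomide dose).** Inputs from 5.3.2: dosing on days 1 to 5; next cycle 28 ± 7 days after the first dose of the preceding one; first post-radiation course 28 ± 7 days after the last day of radiotherapy.
- Between post-radiation courses: next start is day 1 + 28 = 29. Days since last dose = 29 - 5 = 24. Adding the 30-day delay gives 24 + 30 = **54** (47 to 61 with the ±7 window).
- First post-radiation course, assuming the last concomitant dose falls on the last radiotherapy day: 28 + 30 = **58** (51 to 65).
- Against 60, the nominal gap at a cycle start is 60 - 58 = 2 to 60 - 54 = 6 days.
- Hold within a 5-day course: the next dose is due one day after the last, so the Section 6 limit falls at about 1 + 30 = 31 days. The gap is 60 - 31 = **29** days.

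Section 5.3.2 also has a hole of its own. It gives a dosing rule for recovery within 30 days and a stopping rule at 60, but none for recovery between days 31 and 60.

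**5. Reduced dose.** From 200 mg/m2, one level lower is 150, so 5.3.2 and the dose-level table agree. From 150, the 5.3.2 text gives 150 - 150 = 0 reduction, while one level lower in the table is 100.

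**The case against.** The best reply is that 5.3.2 offers guidelines for a standard-of-care drug, so the other sections govern. But no section says so. Section 5.2.3 makes its criteria mandatory, Section 6 says modifications will follow its tables, and 5.3.2 describes its own dosing as part of this protocol.

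It can also be said that 5.3.2 does not actually state that bavituximab continues. That is fair: the conflict there is between a rule that names one drug and rules that end everything. Nor do the tables' temozolomide column headings confine the stop to temozolomide, since the footnote sends the participant off protocol therapy and Section 5.5 uses that term for the participant's treatment as a whole.

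Several stronger readings are tempting but not supported.
- **That Section 6 contradicts itself by letting bavituximab continue.** The text reads naturally in sequence: bavituximab continues during a temporary hold, and protocol therapy ends if the delay passes 30 days.
- **That every patient recovering between days 31 and 60 is handled in opposite ways.** A patient reaching grade 1 on day 40 after the last dose of a 5-day course is 40 - 24 = 16 days into the permitted cycle delay. Neither 5.2.3 nor 5.3.2 stops treatment.
- **That the conflict costs 8 of 18 bavituximab doses (44%).** Cycles 3 and 4 do hold 4 + 4 = 8 weekly doses, in weeks 11 to 18. But bavituximab may continue during the hold, and Section 6 leaves the schedule unchanged. A 30-day delay from the start of cycle 3 uses up about weeks 11 to 14, leaving about 4 of 18 (22%) to lose. From the start of cycle 4 it leaves about none. Only the grade 4 rule, met at the very start of cycle 3, would approach 44%.
- **That the primary analysis is compromised.** Section 13.5.2 specifies intention to treat for OS12, so stopping treatment removes no one.

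**Conclusion.** The protocol is inconsistent as written and should be corrected. The conflicts on recovery grade and on what is stopped hold whichever clock is used. The grade 4 conflict holds for the four tabulated toxicities. The time-limit conflict is small at a cycle start (2 to 6 days nominal, and within the ±7-day window it can vanish or reverse) and about 29 days for a hold within a course. The dose conflict is confined to patients already at 150 mg/m2.

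The consequences are for safety, uniform handling, bavituximab exposure, and off-treatment dates and reasons. Sample size, significance level and power are untouched. The number of patients affected cannot be estimated, because the documents give no rate for persistent grade 2 or for grade 4 toxicity under this regimen. The clock comparison assumes nominal schedules, a full 5-day course and, for the first post-radiation course, temozolomide taken through the last radiotherapy day.

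**What to change.** Reconcile Sections 5.2.3, 5.3.2 and 6 so that each temozolomide toxicity has:
- one recovery grade, used wherever the toxicity is mentioned;
- one time limit with a stated starting point (last dose or scheduled cycle start), leaving no interval without a rule;
- one rule for grade 4 events;
- one explicit statement of whether bavituximab also stops when temozolomide is stopped permanently, kept separate from the existing permission to continue during a temporary hold.

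Make the reduced dose in 5.3.2 agree with the dose-level table for a patient at either starting level. If one section is meant to prevail, say so. Which rule and which dose stand is for the clinical team to decide. The cost is protocol wording in three sections; the design and the primary analysis need no change.
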